#### **5.4.3.3 Abortions**

Any abortion should be classified as a serious adverse event (as the Sponsor considers abortions to be medically significant), recorded on the Adverse Event eCRF, and reported to the Sponsor immediately (i.e., no more than 24 hours after learning of the event; see Section 5.4.2).

#### **5.4.3.4 Congenital Anomalies/Birth Defects**

Any congenital anomaly/birth defect in a child born to a female patient exposed to study treatment or the female partner of a male patient exposed to study treatment should be classified as a serious adverse event, recorded on the Adverse Event eCRF, and reported to the Sponsor immediately (i.e., no more than 24 hours after learning of the event; see Section 5.4.2).

#### **5.4.4 Reporting Requirements for Cases of Overdose, Medication Error, Drug Abuse, or Drug Misuse**

*Overdose (accidental or intentional), medication error, drug abuse, and drug misuse (hereafter collectively referred to as "special situations"), are defined as follows:*

- *Accidental overdose: accidental administration of a drug in a quantity that is higher than the assigned dose*
- *Intentional overdose: intentional administration of a drug in a quantity that is higher than the assigned dose*
- *Medication error: accidental deviation in the administration of a drug*

*In some cases, a medication error may be intercepted prior to administration of the drug.*

- *Drug abuse: intentional excessive use of a drug that may lead to addiction or dependence, physical harm, and/or psychological harm*
- *Drug misuse: intentional deviation in the administration of a drug that does not qualify as drug abuse*

*In cases where drug is to be self administered by the patient, drug misuse could involve the drug being administered to someone other than the patient.*

*Special situations are not in themselves adverse events, but may result in adverse events. Each adverse event associated with a special situation should be recorded separately on the Adverse Event eCRF. If the associated adverse event fulfills seriousness criteria, the event should be reported to the Sponsor immediately (i.e., no more than 24 hours after learning of the event; see Section 5.4.2). For idasanutlin, obinutuzumab or rituximab, and venetoclax, adverse events associated with special situations should be recorded as described below for each situation:*

- *Accidental overdose: Enter the adverse event term. Check the "Accidental overdose" and "Medication error" boxes.*
- *Intentional overdose: Enter the adverse event term. Check the "Intentional overdose" box. If drug abuse is suspected, check the "Drug abuse" box. If drug abuse is not suspected, check the "Drug misuse" box.*
- *Medication error that does not qualify as an overdose: Enter the adverse event term. Check the "Medication error" box.*
- *Medication error that qualifies as an overdose: Enter the adverse event term. Check the "Accidental overdose" and "Medication error" boxes.*
- *Drug abuse that does not qualify as an overdose: Enter the adverse event term. Check the "Drug abuse" box.*
- *Drug abuse that qualifies as an overdose: Enter the adverse event term. Check the "Intentional overdose" and "Drug abuse" boxes.*
- *Drug misuse that does not qualify as an overdose: Enter the adverse event term. Check the "Drug misuse" box.*
- *Drug misuse that qualifies as an overdose: Enter the adverse event term. Check the "Intentional overdose" and "Drug misuse" boxes.*

*In addition, all special situations associated with idasanutlin, obinutuzumab or rituximab, and venetoclax, regardless of whether they result in an adverse event, should be recorded on the Adverse Event eCRF and reported to the Sponsor immediately (i.e., no more than 24 hours after learning of the event). Special situations should be recorded as described below:*

- *Accidental overdose: Enter the drug name and "accidental overdose" as the event term. Check the "Accidental overdose" and "Medication error" boxes.*

- *Intentional overdose: Enter the drug name and "intentional overdose" as the event term. Check the "Intentional overdose" box. If drug abuse is suspected, check the "Drug abuse" box. If drug abuse is not suspected, check the "Drug misuse" box.*
- *Medication error that does not qualify as an overdose: Enter the name of the drug administered and a description of the error (e.g., wrong dose administered, wrong dosing schedule, incorrect route of administration, wrong drug, expired drug administered) as the event term. Check the "Medication error" box.*
- *Medication error that qualifies as an overdose: Enter the drug name and "accidental overdose" as the event term. Check the "Accidental overdose" and "Medication error" boxes. Enter a description of the error in the additional case details.*
- *Intercepted medication error: Enter the drug name and "intercepted medication error" as the event term. Check the "Medication error" box. Enter a description of the error in the additional case details.*
- *Drug abuse that does not qualify as an overdose: Enter the drug name and "drug abuse" as the event term. Check the "Drug abuse" box.*
- *Drug abuse that qualifies as an overdose: Enter the drug name and "intentional overdose" as the event term. Check the "Intentional overdose" and "Drug abuse" boxes.*
- *Drug misuse that does not qualify as an overdose: Enter the drug name and "drug misuse" as the event term. Check the "Drug misuse" box.*
- *Drug misuse that qualifies as an overdose: Enter the drug name and "intentional overdose" as the event term. Check the "Intentional overdose" and "Drug misuse" boxes.*
- *Drug administered to someone other than the patient: Enter the drug name and "patient supplied drug to third party" as the event term. Check the "Drug misuse" box.*

*As an example, an accidental overdose that resulted in a headache would require the completion of two Adverse Event eCRF pages, one to report the accidental overdose and one to report the headache. The "Accidental overdose" and "Medication error" boxes would need to be checked on both eCRF pages.*

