### **5.3.5.12 Adverse Events Associated with an Overdose or Error in Treatment Administration**

An overdose is the accidental or intentional use of a drug in an amount higher than the dose being studied. An overdose or incorrect administration of study treatment is not itself an adverse event, but it may result in an adverse event (*see Section 5.4.4*).

Additionally, all adverse events associated with an overdose or incorrect administration of study treatment should be recorded on the Adverse Event eCRF. If the associated adverse event fulfills seriousness criteria, the event should be reported to the Sponsor immediately (i.e., no more than 24 hours after learning of the event; *see Section 5.4.2*).

No experience with overdose is available from human clinical trials. In clinical trials with obinutuzumab doses ranging from 50 mg up to and including 2000 mg per infusion have been administered. The incidence and intensity of adverse reactions reported in these studies did not appear to be dose dependent.

Limited experience with doses higher than the approved IV doses of rituximab is available from clinical trials in humans. The highest IV dose tested in humans is 5000 mg (2250 mg/m^2). No additional safety signals were identified.

Patients who experience overdose should have immediate interruption or reduction of their infusion and should be closely supervised. Consideration should be given to the need for regular monitoring of blood cell count and for increased risk of infections while patients are B cell depleted.

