## 2.4 Handling of Missing and Incomplete Data

Laboratory values with either a '<' or '>' included in the lab result will have the inequality symbol removed and 0.001 will be either subtracted (when '<' is included) or added (when '>' is included) to the numeric value of the result for the purpose of summarizing (the original value will be displayed in listings). For example, laboratory values given as "<7" or ">7" are treated as follows:

Recorded data value	When reported as numerical value	When reported in a listing
<7	6.999	<7
>7	7.001	>7

Each AE is assigned to a time period, i.e. pre-treatment, during treatment (could be further split as induction/maintenance or consolidation) or follow-up (Section 2.3).

In listings AEs with partial dates will be shown by having a missing study day.

For AEs and concomitant treatment (not including NALTs), the following rules will be applied:

- Incomplete onset dates for AEs will be handled as follows:
  - in case the day is missing, it is replaced by the 1st of the month, unless a trial treatment exists within that month (not necessarily first treatment) then set to the date of that treatment
  - in case the day and month are missing, they are replaced by 1st of January, unless the first trial treatment exists within that year then set to the date of that treatment
  - in case imputation leads to the AE occurring before treatment, the onset date will be set to the treatment start date
  - resolution dates are checked to ensure imputed onset dates do not become later than the resolution date
- In case AE most extreme intensity is missing, it will be replaced by the initial intensity
- AEs with missing grades will be included in the summaries for grade 3 to 5 AEs
- AEs with missing relationship to trial medication are included in the summaries of related AEs
- AE with missing seriousness will be included in all summaries of serious adverse events (SAEs)

- For partial concomitant treatment start dates the 1st of the month will be imputed (if only day is missing) or 1st January will be imputed (if day and month are missing).

Partial dates of NALT will be imputed as follows, in order to use the most conservative (i.e. earliest) date without shortening the treatment period:

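### Special situations that the protocol says are not adverse events are entered as event terms on the Adverse Event eCRF, and the SAP has no rule to keep them out of the AE tables

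*Protocol*

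**What the plan says.** Protocol Section 5.3.5.12: "An overdose or incorrect administration of study treatment is not itself an adverse event". Section 5.4.4 repeats the principle for the whole group: "Special situations are not in themselves adverse events, but may result in adverse events".

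Section 5.4.4 then gives two recording instructions. An adverse event that results from a special situation gets its own entry. Separately, every special situation linked to a study drug, "regardless of whether they result in an adverse event, should be recorded on the Adverse Event eCRF", with the situation itself as the event term. The list of terms covers medication errors caught before administration and drug supplied by the patient to someone else. The section's example is an accidental overdose that causes a headache, which "would require the completion of two Adverse Event eCRF pages, one to report the accidental overdose and one to report the headache". The relevant check boxes are ticked on both pages.

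Protocol Section 6.4 summarises all adverse events from first dose by mapped term and grade. SAP Section 6.2.1 puts all AEs in the listings and, as a general rule, limits AE and SAE summary tables to treatment-emergent events. The SAP text does not mention overdose, medication error, abuse, misuse or special situations, and its update log has no such entry.

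SAP Section 2.4 sets the missing-value rules: "AEs with missing grades will be included in the summaries for grade 3 to 5 AEs". Missing seriousness is counted as serious, and missing relationship as related.

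**The concern.** The Adverse Event eCRF carries two kinds of record: adverse events, and administrative reports that the protocol says are not adverse events. The analysis plan does not separate them. A programmer who builds the AE tables from the form with the one stated filter will count both kinds. A colleague who reads the protocol definition strictly may drop some. The plan does not settle which table is produced.

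The nature, frequency and severity of adverse events is a named safety endpoint in both phases (Protocol Section 2.1), and the Internal Monitoring Committee reviews cumulative safety data. An intercepted error, where nothing was administered, says nothing about tolerability.

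The protocol shows elsewhere that it can keep a reportable non-AE off this form: Section 5.4.3.1 sends pregnancies to a separate reporting form and keeps them off the Adverse Event eCRF. Special situations are not treated that way, so the separation has to be made in the analysis.

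**Working it through.** The plan states no figure to reproduce. The check traces the rules and counts records.

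1. **Record count in the protocol's example.** Pages for the special situation: 1. Pages for the resulting headache: 1. Total 1 + 1 = 2 AE records for 1 adverse event. With special-situation-only records excluded, the count returns to 1. For an intercepted error there is 1 record and 0 adverse events.

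2. **Route into the all-grade tables.** Such a record dated on or after first dose passes the only general filter in SAP Section 6.2.1. It then adds to the total number of AEs (Outputs 36 and 37), the by-cycle counts (Output 45) and the row for its own coded term.

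3. **Weight of one patient.**
   - Expansion cohort of 40 (Protocol Section 6.1.2): 1/40 = 2.5 points; 2/40 = 5.0; 4/40 = 10.0. Two patients with the same coded term reach the 5% threshold of Output 49.
   - Escalation cohort of 3 to 6 (Protocol Section 3.1.2): 1/6 = 17% to 1/3 = 33% for that term.

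4. **Route into the Grade 3 to 5, serious and related tables.** This depends on blank fields.
   - Fields completed, for example low grade and not serious: the missing-value rules add 0.
   - Grade blank: counted as Grade 3 to 5. SAP Section 2.4 first fills a blank most extreme intensity from the initial intensity, so both must be blank.
   - Seriousness blank: counted as serious. Relationship blank: counted as related. Each acts separately.

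5. **Illustration of the blank-grade case.** Let g be the true proportion of patients with a Grade 3 to 5 event and q the proportion with a blank-grade special-situation record, taken as independent. Reported proportion = g + (1 − g)q, so the excess is (1 − g)q. Both g and q are assumptions; the documents give neither.
   - g = 0.50, q = 0.10: 0.50 + 0.50 × 0.10 = 0.55, an excess of 5 points.
   - g = 0.90, q = 0.05: 0.10 × 0.05 = 0.005, an excess of 0.5 points.
   - g = 0.30, q = 0.20: 0.70 × 0.20 = 0.14, an excess of 14 points.

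6. **Can the check boxes separate the records?** No. In the example they are ticked on both the overdose page and the headache page. A filter on the boxes alone would also remove the headache. The event term is what distinguishes the two.

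**The case against.** The strongest reply is that both documents summarise adverse events, and the protocol says special situations are not adverse events, so they are already outside the tables. The SAP also relies on a List of Planned Outputs and company standards that are not available here and could hold an exclusion. This stands to the extent that inclusion follows from the recording rule and the SAP's silence, not from an explicit instruction to count them. It does not remove the defect: the SAP text that sets the filter names only treatment emergence.

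A second reply is that Protocol Section 5.3 requires seriousness, severity and causality for each adverse event on the form, that Table 20 offers a Grade 1 for events outside CTCAE, and that Section 7.1 provides for data queries. A reader might infer that Grade 3 to 5 and serious counts will be inflated. The documents do not support that as fact, because nothing says these fields are left blank. Equally, Section 5.3 is silent on entries that are not adverse events, and Output 43 has rows for missing grade and missing seriousness, so blanks are contemplated.

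Third, the row for patients with at least one AE has little room to move. All 99 patients in Study NP27872, all 122 in NP28679 and 9 of 10 in GH29914 had one. This stands: event totals and term-level incidence are what change.

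Fourth, a reader might infer from the definition "Medication error: accidental deviation in the administration of a drug" that every missed tablet becomes an AE record. Section 5.4.4 does not name missed doses among its examples. Sections 4.3.2.3 and 4.3.2.4 treat them as a dosing instruction, and Section 3.1.2 uses them for DLT evaluability. None of these points to Section 5.4.4.

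**Conclusion.** The concern holds as a gap between a stated recording rule and an analysis plan that does not account for it. AE tables built from the Adverse Event eCRF count records that the protocol defines as non-events. The certain part is small and structural: two records for one headache, and a full record for an intercepted error. Inflation of Grade 3 to 5, serious or related counts is conditional on blank fields. The 0.5 to 14 point range is an illustration over assumed inputs, not an estimate.

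The overall size cannot be computed. A reader might try multiplying an error rate by the number of oral doses. The documents give no rate, and the dose count depends on the regimen. With oral dosing in all six cycles it is 6 × 5 = 30 idasanutlin plus 30 to 60 venetoclax doses, or 60 to 90. Under Regimen B, with oral dosing in Cycles 2 to 6 only, it is 25 plus 25 to 50, or 50 to 75. For the same reason, a bias between the Days 1–5 and Days 1–10 venetoclax schedules is not established.

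Nor does the problem reach the dose model. DLTs have their own criteria in Section 3.1.2.1, and the mCRM uses DLT occurrence, not AE counts. What is affected is the descriptive safety reporting of a named endpoint.

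**What to change.** Add to SAP Section 6.2.1 a rule along these lines. Records whose event term is only the special situation itself (overdose, medication error, intercepted error, abuse, misuse or supply to a third party) are excluded from the AE, Grade 3 to 5, related-AE, SAE, by-cycle and safety-summary outputs, and the missing-value rules in Section 2.4 do not apply to them. They appear in a separate special-situations listing. Any adverse event that results from a special situation stays in the AE tables.

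Identify these records by a coded-term list or a record-level flag, not by the check boxes alone. Medication errors that are not overdoses are entered as a description of the error, so the list or flag needs review as data accrue.

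The cost is a short SAP paragraph, one extra listing, and upkeep of the term list or flag. Immediate reporting to the sponsor is unchanged, and with a coded-term list so is data collection.

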## **5.5 FOLLOW-UP OF PATIENTS AFTER ADVERSE EVENTS**

### **5.5.1 Investigator Follow-Up**

The investigator should follow each adverse event until the event has resolved to baseline grade or better, the event is assessed as stable by the investigator, the patient is lost to follow-up, or the patient withdraws consent. Every effort should be made to follow all serious adverse events considered to be related to study treatment or trial-related procedures until a final outcome can be reported.

During the study period, resolution of adverse events (with dates) should be documented on the Adverse Event eCRF and in the patient's medical record to facilitate source data verification.

All pregnancies reported during the study should be followed until pregnancy outcome.

### **5.5.2 Sponsor Follow-Up**

For serious adverse events, adverse events of special interest, and pregnancies, the Sponsor or a designee may follow-up by telephone, fax, electronic mail, and/or a monitoring visit to obtain additional case details and outcome information (e.g., from hospital discharge summaries, consultant reports, autopsy reports) in order to perform an independent medical assessment of the reported case.

### **5.6 ADVERSE EVENTS THAT OCCUR AFTER THE ADVERSE EVENT REPORTING PERIOD**

After the end of the adverse event reporting period (defined as 90 days after the last dose of study drug), all deaths, regardless of cause, should be reported on the Long-Term Survival Follow-Up eCRF. Grade 3 and 4 infections (related and unrelated) in patients who received obinutuzumab should be reported on the Adverse Event eCRF until up to 2 years after the last dose of obinutuzumab. In addition, if the investigator becomes aware of a serious adverse event that is believed to be related to prior study treatment, the event should be reported through use of the Adverse Event eCRF. The sponsor should also be notified of events of second malignancies indefinitely (even if the study has been closed) for patients who received obinutuzumab.

The investigator should report any other events (excluding related serious adverse events 90 days after the last dose of study treatment if the investigator becomes aware of any event and Grade 3 and 4 infections, independently of causality, for 2 years) directly to the Sponsor or its designee, either by faxing or by scanning and emailing the Serious Adverse Event/Adverse Event of Special Interest Reporting Form using the fax number or email address provided to investigators.

During survival follow-up, deaths attributed to progression of lymphoma should be recorded only on the Study Completion/Early Discontinuation eCRF.

### **5.7 EXPEDITED REPORTING TO HEALTH AUTHORITIES, INVESTIGATORS, INSTITUTIONAL REVIEW BOARDS, AND ETHICS COMMITTEES**

The Sponsor will promptly evaluate all serious adverse events and adverse events of special interest against cumulative product experience to identify and expeditiously communicate possible new safety findings to investigators, IRBs, ECs, and applicable health authorities based on applicable legislation.

To determine reporting requirements for single adverse event cases, the Sponsor will assess the expectedness of these events using the following reference documents:

- Obinutuzumab Investigator's Brochure
- Rituximab IV Oncology Investigator's Brochure
- Idasanutlin Investigator's Brochure
- Venetoclax Investigator's Brochure

The Sponsor will compare the severity of each event and the cumulative event frequency reported for the study with the severity and frequency reported in the applicable reference document.

Reporting requirements will also be based on the investigator's assessment of causality and seriousness, with allowance for upgrading by the Sponsor as needed.

## **6. STATISTICAL CONSIDERATIONS AND ANALYSIS PLAN**

Study data will be summarized separately for dose escalation and expansion phase. Data from the dose-escalation phase will be summarized by dose level and regimen. Data from the expansion phase will be summarized by histologic subtype (i.e., FL or DLBCL).

### **6.1 DETERMINATION OF SAMPLE SIZE**

#### **6.1.1 Dose Escalation**

Dose finding will be conducted during the dose-escalation phase of this study. The estimated sample size follows from the dose-escalation rules for a mCRM with over dose control ([Thall et al. 2003](#); [Neuenschwander et al. 2015](#)). It is anticipated that enrollment of up to eight cohorts of 3–6 patients each, for a total of 9–60 patients, will be required to meet the Part 1 study objective. This number is an approximation based upon assumptions and experience from other similar dose-finding studies. More details on the dose-escalation design and its operating characteristics are given in [Section 3.1.2.3](#) and [Appendix 6](#). The estimated probability to require more than 50 patients in the investigated scenarios in the protocol is generally <5%.

#### **6.1.2 Expansion Cohorts**

Approximately 80 patients (40 patients with FL and 40 patients with DLBCL) will be enrolled during the expansion phase.

The primary efficacy analysis for the expansion phase will be estimation of the true proportion of patients expected to obtain a PET-defined CR at EOI. A sample size of 40 patients is deemed sufficient to provide adequate precision for the point estimate and for the lower end of the 90% CI to rule out a clinically uninteresting probability of response of <40% in FL, and 40% in DLBCL assuming an observed PET-defined CR rate of 55%. [Table 21](#) provides 90% Clopper-Pearson exact CIs for the probability of

achieving a PET-defined CR at the EOI for a range of observed proportions based on a sample of 40 patients.

**Table 21 Potential 90% CI for the True Probability of Achieving a PET-CT-Defined Complete Response at End of Induction for n=40**

Observed Proportion of Patients Achieving a PET-CT-Defined CR at EOI	Two-Sided 90% Clopper-Pearson CI a for True Population PET-CT-Defined CR
0.32	(0.20, 0.46)
0.50	(0.36, 0.64)
0.55	(0.40, 0.68)
0.60	(0.46, 0.73)
0.65	(0.51, 0.77)
0.70	(0.56, 0.82)
0.72	(0.58, 0.83)
0.75	(0.61, 0.86)
0.80	(0.66, 0.89)
0.85	(0.72, 0.93)

CI = confidence interval; CR = complete response; CT = computed tomography; EOI = end of induction; PET = positron emission tomography.

a Note that the lower limit of a two-sided 90% CI is equivalent to a one-sided 95% CI limit.

